### 8.4.4 12-Lead ECG

**Per dosing session:** Baseline is defined as the measurements of pre-initial dose during each dosing session.

**Per participant:** Baseline is defined as the measurements collected at Visit 1. Post-baseline ECG was collected at Visit 15.

Where multiple values (e.g. triplicate ECG) are recorded at a time for a participant, the mean of the values will be used in the descriptive statistics.

Descriptive statistics for the actual values and changes from baseline will be calculated for each parameter by treatment and timepoint. The shift table (clinical significance) is used to describe the changes of 12-Lead ECG results prior and post dose at each timepoint.

Standard 12-lead ECG parameters (PR, QRS, QT, QTcF intervals, and HR) will be listed for individual participants.

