### 1.3 Schedule of Assessments (SoA)

	Screening		Treatment Period												Follow-Up Period					ET
Visit Number	1	2	3	4	5	6	7	8	9	10	11	12	13	14	15	16	17	18	19	-
Visit Session	ScrN	BL/ Prep	Treatment 1			Treatment 2			Treatment 3			Treatment 4			FU1	FU2	FU3	TC	FU4 /EOS	ET visit
Study Day(s)	-28 to BL	-4 to - 1	1	2	3 (+1)	8 (±1)	9	10 (+1)	15 (±1)	16	17 (+1)	22 (±1)	23	24 (+1)	29 (±1)	36 (±2)	43 (±2)	57 (±2)	64 (±3)	-
ICF	X																			
Demography	X																			
Confirm Eligibility	X	X	X																	
Med Hx	X																			
Substance Use Hx	X																			
Drug Use Assessment 	X	X	X			X	X		X			X								
Pregnancy Test 	X		X			X	X		X			X			X					X 
Physical Exam	X 														X				X 	X 
Vital Signs 	X	X	X 			X 			X 			X 			X					X 
12-Lead ECG	X		X 			X 			X 			X 			X					X 
Clinical Labs 	X								X						X					X 
MINI (central rater)	X																			
LEC-5	X																			
SPQ	X																			
SCID-5-PD (Central rater) 	X																			
CAPS-5 (past month; central rater)	X																			
C-SSRS 	X	X	X	X	X	X	X	X	X	X	X	X	X	X	X	X	X	X	X	X
Preparatory Session 		X																		
Randomization 			X																	
Study Drug Admin 			X			X			X			X								

 Urine drug screen must be confirmed as negative prior to enrollment and each dose. Site must confirm patient is not otherwise impaired prior to dosing.

 Urine test for WOCBP only. Pregnancy test must be confirmed as negative prior to enrollment and each dose. Serum FSH may be conducted at Screening to confirm non-childbearing potential.

 Only required if the ET visit occurs prior to the Day 29 visit.

 Height and weight will be collected at Screening; weight will be conducted at the end of study.

 Includes heart rate, blood pressure, and temperature.

 Vital signs during the dose session: BP and HR - predose, every 30-minutes post-initial dose, and prior to the booster dose; temperature- predose (within 10 min), and every 60 minutes.

 ECGs will be captured predose and at the end of the dosing session.

 Clinical labs will be assessed by a central lab.

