## 4.2 Study Visit Breakdown

Screening Period		
Study Visit	Visit Timing	Brief Description of Events
Screening (Visit 1)	Day -28 to Baseline	
Obtain informed consent and assess all Screening measures including Clinician Administered PTSD Scale for DSM-5 (CAPS-5; past month version), MINI 7.0.2, PCL-5, LEC-5, SPQ (and SCID-5-PD, if needed) C-SSRS, demographics and medical history, substance use history and pre-study medications.
 
The CAPS-5, MINI, and SCID-5-PD (if needed) will be administered by the Central rater and recorded for rater fidelity.
 
Physical examinations (including height and body weight), vital signs, temperature, 12-lead ECG, and labs (including safety labs, urine drugs test, and pregnancy test [women of childbearing potential (WOCBP) only, see Section 14.4], plus serum follicle stimulating hormone [FSH] test [if needed, see Section 14.4]) and a review of eligibility criteria will also be performed.

Baseline/Preparatory Session		
Study Visit	Visit Timing	Brief Description of Events
Baseline/Preparatory Session (Visit 2)	Day -4 to Day -1	
Baseline: The following safety assessments will be assessed prior to evaluations by the central rater to ensure the participant continues to meet eligibility requirements: urine drugs test, vital signs, concomitant medication review, and C-SSRS.
 
Central rater scales will be administered via telephone/video; the CAPS-5 will be performed first followed by MADRS and CGI-S. The CAPS-5, MADRS, and CGI-S will be recorded for rater fidelity.
 
This will be followed by the participant completing the self-administered psychometric assessments (PCL-5, BDI-II, SDS, WEMWBS, and PGI-S) as well as the PSQI and PTGI. The order of completion should be: Central rating scales and then the participant reported scales.
 
Preparatory Session: The following session is to be performed after all baseline assessments have been performed:
 
 
• Psychoeducation session, conducted by a trained dosing session monitor. The dosing session monitor will proactively provide the participant with an understanding of the anticipated experience following administration of an entactogen medication, like methylone.
 
 
If needed, a second preparatory session may occur prior to first dosing to ensure the participant is adequately prepared for the treatment period.

Treatment Period		

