### 4.3 Planned Duration of Study

The expected duration of participation for each participant who completes all study visits, from Screening to the EOS visit, is up to 16 weeks. The treatment duration for both Part A and Part B of the study are expected to be the same, as procedures are identical.

- Screening may take up to 28 days.

- The Baseline/Preparatory Period could last up to 4 days and should not be performed >4 days prior to Day 1.
- Enrollment confirmation will take place prior to dosing on Day 1; once enrollment has been confirmed, the Treatment Period will commence.
- The 4-week Treatment Period will consist of four dose sessions 1 week apart, with a telephone visit 1 day after each dose session for collection of safety assessments (AEs, concomitant medications, and C-SSRS) and a follow-up visit to assess safety and efficacy 2 days after each dose session.
- After the final session of the Treatment Period (Visit 14), participants will enter the Follow-Up period. Participants will attend a Follow-Up visit and a Reflection Session approximately 1, 2 and 3 weeks after the final study drug administration, followed by an EOS visit 6 weeks after the final study drug administration. Participants will also be contacted via telephone for collection of safety assessments on Day 57 ( $\pm 2$  days).
- Participants withdrawing before completion of the study should be encouraged to attend a visit that would duplicate the EOS visit to collect safety and efficacy information.

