### 5.5.1 Prohibited Medications

No formal drug interaction studies with methylone have been conducted in man. Based on the mechanism of action and metabolism of methylone, drug interactions between methylone and other psychoactive substances are possible.

The following medications are prohibited within 8 weeks, or 5 half-lives, whichever is longer of Day 1 and through the End of Study visit:

- Selective serotonin reuptake inhibitor (SSRIs)
- Serotonin and norepinephrine reuptake inhibitors (SNRIs)
- Tricyclic/tetracyclic antidepressants
- Other medications to treat PTSD

The following medications are prohibited within 14 days or 5 half-lives, whichever is longer of Day 1 and through the End of Study visit:

- Lithium and other mood stabilizers
- Antipsychotics
- Stimulants
- Efavirenz
- Strong CYP2D6 inhibitors or inducers
- Serotonin-acting dietary supplements (such as 5-hydroxy-tryptophan or St. John's wort)
- QT-prolonging medications (such as antiarrhythmics and some antibiotics)

The following are restricted within 24 hours of a dosing session:

- Benzodiazepines
- Opioids
- Alcohol

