  - b. Moderate or severe alcohol use disorder (as assessed by the MINI Version 7.0.2) *Note: Moderate alcohol use disorder in early remission is not exclusionary:*
    - i. the inability to refrain from alcohol use for 24 hours before Screening and each scheduled dose session.
  - c. Medical or psychiatric condition that is incompatible with:
    - i. establishment of rapport with the dosing session monitor, or
    - ii. safe exposure to methylone.
13. Prior treatment within the 90 days prior to Baseline, with:
  - a. deep brain stimulation,
  - b. vagus nerve stimulation,
  - c. treatment with electroconvulsive therapy, or
  - d. transcranial magnetic stimulation.

14. Use of a psychedelic (e.g., lysergic acid diethylamide [LSD], psilocybin, dimethyltryptamine [DMT], mescaline), or entactogens such as MDMA, within 12 months of Screening.
15. Use of prohibited concomitant medications or therapies (see [Section 5.5.1](#)).
16. Current or previous history of clinically significant cardiovascular/cerebrovascular conditions.
  - a. Presence of underlying cardiovascular or cerebrovascular conditions where an acute rise in blood pressure would pose a clinical concern, including but not limited to, aneurysms or arteriovenous malformations, a history of cardiac or cerebral ischemia.
17. Any clinically significant abnormal 12-lead ECG findings at Screening.
  - a. Resting QT interval corrected for heart rate using Fridericia's formula (QTcF)  $\geq 450$  msec for males,  $\geq 470$  msec for females at Screening, or inability to determine QTcF interval.
  - b. Presence of risk factors for Torsades de Pointes.
18. Any history of head injury with loss of consciousness for more than 30 minutes within 12 months of Screening.
19. Clinically relevant history of schizophrenia, psychotic disorder, bipolar disorder, delusional disorder, paranoid personality disorder, antisocial personality disorder, schizoaffective disorder, borderline personality disorder or panic disorder, as assessed by the MINI and SPQ (and SCID-5-PD, if needed).
20. Have a first-degree relative with:
  - a. schizophrenia spectrum, or
  - b. other psychotic disorders (except substance/medication-induced or due to another medical condition), or
  - c. Bipolar I disorder.
21. Participant has participated in a clinical study with an IMP within 3 months, or 5 half-lives (whichever is longer), prior to Screening.

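### The Visit 15 ECG comparison takes its baseline from the Screening tracing used for eligibility, so a finding already present before the first dose can count as a change on study

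*SAP*

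**What the plan says.** SAP 8.4.4 defines two ECG baselines. Within a dosing session, "Baseline is defined as the measurements of pre-initial dose during each dosing session". Across the study, per participant, "Baseline is defined as the measurements collected at Visit 1", and the post-baseline tracing is the one at Visit 15. The section then plans descriptive change from baseline and a shift table on clinical significance. The general rule in SAP 8.1.3 (worst pre-treatment value) gives way wherever an endpoint has its own definition, and 8.4.4 supplies one.

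Protocol 4.2 identifies Visit 1 as Screening, and Protocol 4.3 adds: "Screening may take up to 28 days". The schedule in Protocol 1.3 places ECGs at Visit 1, on the four dosing days, at Visit 15, and at an early termination visit that falls before Day 29. There is none at Visit 2. For dosing days, footnote 7 says: "ECGs will be captured predose and at the end of the dosing session". Protocol 7.2 puts the predose tracing within about 30 minutes of dosing.

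Exclusion 17 in Protocol 6.2 removes anyone with "Any clinically significant abnormal 12-lead ECG findings at Screening", including QTcF of 450 ms or more in males and 470 ms or more in females. Protocol section 6 allows no exceptions to the criteria.

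On medication, exclusion 15 points to Protocol 5.5.1, whose list includes QT-prolonging drugs: "The following medications are prohibited within 14 days or 5 half-lives, whichever is longer of Day 1 and through the End of Study visit". Appendix 3 (Protocol 14.3), which Protocol 5.5 also cites, lists QT-prolonging drugs as well, but counts a window of the same length back from Screening.

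Clinically significant ECG change is a Part B safety endpoint (Protocol Table 2; SAP 8.4). SAP 8.4 plans no formal safety testing.

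**The concern.** A baseline for a safety shift table should show the participant's state just before exposure. Here the Visit 15 comparison starts from a tracing that may be four weeks older than the first dose and that also decided eligibility. A later pre-dose tracing is available and is not used for this purpose.

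Two things follow. Anything that arises between Screening and the first dose is credited to the on-study period. And because participants were selected on the baseline tracing itself, the table can only show stability or worsening in clinical significance, never a pre-existing abnormality. Elsewhere the SAP draws the line at the first dose: its TEAE definition (8.4.1) requires onset on or after first administration. The ECG table does not follow that line.

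The stake is modest. Visit 15 is the only scheduled ECG after the last dosing day, so this comparison is the plan's main summary of ECG change that persists after treatment. With no formal tests, the within-arm means and shift counts are what readers will see.

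**Working it through.** The plan states no figure for this comparison, so there is nothing to reproduce. The check is day counting, the logic of the shift table, and an illustration of selection on the baseline.

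**1. Interval.** The schedule runs from Day -1 to Day 1, so I assume there is no Day 0.
- Day -28 to Day 1: 28 days. Day 1 to Day 29: 28 days.
- Screening baseline to Visit 15: up to 28 + 28 = 56 days nominally. Day 1 baseline to Visit 15: 28 days.
- The ±1 day window at Visit 15 moves each by one day.

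**2. Shift table.** CS means clinically significant abnormality. I read the per-participant baseline as the one that governs Visit 15, since 8.4.4 pairs the two.

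| Visit 1 | Day 1 predose | Visit 15 | Result, Visit 1 baseline | Result, Day 1 baseline |
|---|---|---|---|---|
| CS | – | – | excluded by criterion 17 | excluded by criterion 17 |
| not CS | CS | CS | new shift | no shift |
| not CS | CS | not CS | no shift | improvement |
| not CS | not CS | CS | new shift | new shift |

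The second row is possible because exclusion 17 acts only at Screening, and Protocol 4.2 places the Day 1 predose ECG after randomization. The second and fourth rows give the same result under the SAP's definition, although only the fourth is a change since first dose. With about 32 per arm, one such participant moves an arm's shift rate by 1/32 = 3.1 percentage points. The documents give no rate for ECG abnormalities at Day 1, so the expected number is unknown.

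**3. Selection on the QTcF limit.** If QTcF has the same mean and SD at both visits and correlation ρ between them, removing values at or above a cutoff c at the first visit produces a spurious mean rise at the second of

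(1 − ρ) × SD × φ(a)/Φ(a), with a = (c − mean)/SD.

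Assumed inputs, none from the documents: mean 405 to 425 ms, SD 15 to 20 ms, ρ 0.5 to 0.8.
- c = 450, mean 405, SD 15, ρ 0.8: a = 3, rise 0.01 ms.
- c = 450, mean 425, SD 20, ρ 0.5: a = 1.25, rise 2.04 ms.
- c = 470, same grid: 0.00 to 0.32 ms.

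This shows direction and order of size only. The selection precedes randomization, so it is expected equally in both arms.

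**4. Medication window.**
- Protocol 5.5.1, minimum 14 days counted from Day 1: a Screening ECG can be 28 days before Day 1, so 28 − 14 = up to 14 days of Screening lie outside the window.
- Appendix 3, same length counted from Screening: 0 days lie outside it.

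Only under 5.5.1 could the baseline ECG be recorded before a QT-prolonging drug was stopped. The two passages cannot both stand for those drugs. A Day 1 baseline falls inside the window under either.

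**The case against.** The choice can be defended. Visit 1 and Visit 15 are the only scheduled ECGs on non-dosing days apart from early termination, so both are taken away from the anticipation of a dosing day. The SAP treats vital signs similarly, pairing Visit 2 with Visit 15 although Day 1 predose vital signs exist. Acute ECG effects are judged within session against the predose tracing, so a finding at Day 1 predose should be visible in the session 1 output. The safety objective is a comparison with placebo, and anything that happens before randomization falls on both arms alike in expectation. All of this stands. It confines the defect to the Visit 1 to Visit 15 change and shift table. It does not give that table a way to tell a finding that predates the first dose from one that follows it.

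A reader might go further and infer that baseline QTcF is inflated by drugs later withdrawn, so that the plan leans toward showing no prolongation. Assuming that 5 to 20% of participants stop such a drug and QTcF falls by 5 to 20 ms in each, the mean change would shift by −0.05 × 5 = −0.25 ms to −0.20 × 20 = −4 ms. The documents do not support that range. Neither input is in them, and under Appendix 3 the share for the drugs it lists is zero. Other text also makes such cases less likely: Protocol 5.5 requires abstinence from drug treatment of mental conditions from Screening, inclusion 7 says nobody will be asked to stop potentially beneficial treatment, and exclusions 16 and 17 remove significant cardiovascular conditions and risk factors for Torsades de Pointes. Selection at Screening also pushes mean change the opposite way.

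**Conclusion.** The point holds in a limited form. The per-participant ECG baseline is the eligibility tracing, so its clinically significant row is empty for every correctly enrolled participant, and the Visit 15 table cannot separate findings that predate study drug from findings that follow it. This rests on the text of SAP 8.4.4 and exclusion 17 and does not depend on medication use.

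The effect on mean change has no supported size. Its sign is uncertain, it is likely to be small, and it is expected to be the same in both arms. Neither a systematic bias in the comparison with placebo nor a tilt toward no prolongation can be concluded. No sample size, power or efficacy result is affected. This is a minor improvement, worth making because it is cheap.

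The conflict between Protocol 5.5.1 and Appendix 3 is a separate matter. I take no position on which window is right.

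**What to change.** In SAP 8.4.4, define the per-participant ECG baseline as the last ECG before the first dose, which is the Day 1 predose tracing at Visit 3, with Visit 1 only if that tracing is missing. Use it for both the Visit 15 change and the Visit 15 shift table. The per-session baseline stays as it is.

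The change is one line, needs no new data, and puts the boundary at first dose as in the TEAE definition. It has two small costs: anticipation before dosing may raise heart rate on the baseline tracing (QTcF is rate-corrected), and the pairing of two non-dosing-day ECGs is lost.

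Separately, the sponsor should reconcile the QT-prolonging drug windows in Protocol 5.5.1 and Appendix 3. The baseline change need not wait for that.

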### 8.4.5 Physical Examination

Shift table (clinical significance) is used to describe the changes of physical examination prior and post dose visit. Abnormal findings of physical examination data will be listed by participant.

### 8.4.6 C-SSRS

The number and percentage of subjects with suicidal ideation (Category 1-5) or suicidal behavior (Category 6-10), and Self-injurious behavior without suicidal intent based on the C-SSRS after first administration of study drug will be summarized.

Two shift tables will demonstrate changes in C-SSRS, most severe suicidal ideation (0 to 5), and C-SSRS categories (No suicidal ideation or behavior, suicidal ideation, suicidal behavior) from baseline to post-treatment.

C-SSRS results will be listed for individual participants.

[REDACTED]

## 9 DESCRIPTION OF STATISTICAL ANALYSIS PLAN

This SAP describes the analysis for Part B of the IMPACT-1 study. The planned analyses identified in this SAP may be included in regulatory submissions and/or future manuscripts. Exploratory analyses, not identified in this SAP, may be performed to support the clinical development program. Any post-hoc or unplanned analyses that are performed but not identified in this SAP will be clearly identified in the clinical study report (CSR).

### 9.1 Changes from the Protocol Specified Statistical Analyses

This SAP is drafted on the basis of the content in the protocol.

There are some changes from the protocol:

1. This SAP includes additional derivative analysis of the CAPS-5 and MADRS scores, which are not directly described in the current protocol.
2. The SAP Section 7 added missing data or data imputation methods.
3. Protocol Section 9.5.1.5: Physical examination data will be listed by participant for abnormal findings only. In the SAP, Section 10.3.5: Shift table (clinical significance) is used to describe the changes of physical examination prior and post dose.
4. SDS in protocol is “a total score from 0 to 30, where 0-Unimpaired and 30-Highly impaired.” In the SAP, mean of each of the 3 domains (0-10) has been used.
5. The definition of ITT population has been revised to mITT population.
6. All tests will be based on “one-sided significant level of 0.05” instead of “two-sided significant level of 0.05”.
7. Add sex as a covariate. The endpoints baseline (if applicable) and sex will be as covariates in the analysis model.

In consideration of unpredictable changes of final data collection in the clinical trial, there may be minor adjustments to this SAP.

## 11 APPENDIX

### 11.1 Appendix 1 Scoring Instructions for the PSQI

The PSQI contains 19 self-rated questions. Only self-rated questions are included in the scoring. The 19 self-rated items are combined to form seven component scores, each of which has a range of 0-3 points. In all cases, a score of 0 indicates no difficulty, while a score of 3 indicates severe difficulty. The seven component scores are then added to yield one global score, with a range of 0-21 points, 0 indicating no difficulty and 21 indicating severe difficulties in all areas.

- **Component 1: Subjective sleep quality**

Question #6, and assign scores as follows:

Response	Component 1 score
Very good	0
Fairly good	1
Fairly bad	2
Very bad	3

Component 1 score: \_\_\_\_\_

- **Component 2: Sleep latency**

1. Question #2, and assign scores as follows:

Response	Score
≤15 minutes	0
16-30 minutes	1
31-60 minutes	2
> 60minutes	3

2. Question #5a, and assign scores as follows:

Response	Score
Not during the past month	0
Less than once a week	1
Once or twice a week	2
Three or more times a week	3

3. Add #2 score and #5a score

4. Assign component 2 scores as follows

Sum of #2 and #5a	Component 2 Score
0	0
1-2	1
3-4	2
5-6	3

Component 2 score: \_\_\_\_\_

- **Component 3: Sleep duration**

Question #4, and assign scores as follows:

Response	Component 3 Score
>7 hours	0
6-7 hours	1
5-6 hours	2
<5 hours	3

Component 3 score: \_\_\_\_\_

• **Component 4: Habitual sleep efficiency**

1. Write the number of hours slept (question #4) here:
2. Calculate the number of hours spent in bed:  
 Number of hours spent in bed: Getting up time (question #3)-Bedtime (questions #1)
3. Calculate habitual sleep efficiency as follows:  
 Habitual sleep efficiency (%) = (Number of hours slept/Number of hours spent in bed)\*100
4. Assign component 4 scores as follows:

Habitual sleep efficiency (%)	Component 4 Score
>85	0
75-84	1
65-74	2
<65	3

Component 4 score:\_\_\_\_\_

• **Component 5: Sleep disturbances**

1. Question #5b-5j, and assign scores for each question as follows:

Response	Score
Not during the past month	0
Less than once a week	1
Once or twice a week	2
Three or more tiems a week	3

2. Sum of #5b-5j: Add the scores for questions #5b-5j
3. Assign component 5 score as follows:

Sum of # 5b-5j	Component 5 Score
0	0
1-9	1
10-18	2
19-27	3

Component 5 score:\_\_\_\_\_

• **Component 6: Use of sleeping medication**

Question #7 and assign scores as follows:

Response	Component 6 Score
Not during the past month	0
Less than once a week	1
Once or twice a week	2
Three or more times a week	3

Component 6 score:\_\_\_\_\_

• **Component 7: Daytime dysfunction**

1. Question #8, and assign scores as follows:

Response	Score
Never	0
Once or twice	1
Once or twice each week	2
Three or more times each week	3

2. Questions #9, and assign scores as follows:

Response	Score
No problem at all	0
Only a very slight problem	1
Somewhat of a problem	2
A very big problem	3

3. Sum of #8 and #9: Add the scores for question #8 and #9

4. Assign component 7 scores as follows

Sum of #8 and #9	Score
0	0
1-2	1
3-4	2
5-6	3

Component 7 score:\_\_\_\_\_

- **Global PSQI Score:** Add the seven component scores together.

